10.3.3 NON-TARGET LESIONS

Any other measurable and abnormal nodal lesions not selected for quantitation as target lesions may be considered non-target lesions. In addition, non-measurable evidence of CLL/SLL such as nodal lesions with both diameters <1.0 cm, extra-nodal lesions, bone lesions, leptomeningeal disease, ascites, pleural or pericardial effusions, lymphangitis of the skin or lung, abdominal masses that are not confirmed and followed by imaging techniques, cystic lesions, previously irradiated lesions, and lesions with artifacts may be considered as non-target disease.

The presence or absence of non-target disease should be recorded at baseline and as per the study assessment schedule. If present at baseline, up to 6 non-target lesions should be recorded. The non-target disease at baseline will be used as a general reference to further characterize regression or progression of CLL/SLL during assessments of the objective tumor response during treatment. Measurements are not required, and these lesions should be followed as "present" or "absent".

10.4 DEFINITIONS OF TUMOR RESPONSE AND PROGRESSION

Responses will be categorized as CR, CRi, nPR, PR, SD, or PD. In addition, a response category of not evaluable (NE) is provided for situations in which there is inadequate information to otherwise categorize response status, and partial response with lymphocytosis (PR-L) for subjects who have an elevated absolute lymphocyte count but otherwise meet all criteria for a PR.

The best overall response will be determined. The best overall response is the best response recorded from the start of treatment until disease/recurrence progression (taking as a reference for disease progression the smallest measurements recorded since treatment started).

10.4.1 COMPLETE RESPONSE

To satisfy criteria for a CR, all of the following criteria must be met:

- No evidence of new disease
- ALC in peripheral blood of <4 x 10⁹/L
- Regression of all nodal masses to normal size <1.5 cm in the LD
- Normal spleen and liver size
- No constitutional symptoms

U2-VEN-207

- Cytological or pathological evaluation of the BM smear or biopsy must be at least normocellular for age, without evidence for typical CLL/SLL lymphocytes by morphological criteria. This evaluation is not based on a flow cytometry–based MRD assessment
- Peripheral blood counts meeting all the following criteria:
 - ANC \geq 1.5 x 10 $^{\circ}$ /L without need for exogenous growth factors (e.g., G-CSF);
 - Platelet count $\ge 100 \times 10^9$ /L without need for exogenous growth factors;
 - o Hemoglobin ≥110 g/L (11.0 g/dL) without red blood cell transfusions or need for exogenous growth factors (e.g., erythropoietin);

10.4.2 COMPLETE RESPONSE WITH INCOMPLETE MARROW RECOVERY (CRI)

Subjects who fulfill all the criteria for a CR (including BM criteria) but who have a persistent anemia, thrombocytopenia, or neutropenia or a hypocellular BM that is related to prior or ongoing drug toxicity (and not to CLL/SLL) will be considered as a CR with incomplete marrow recovery (CRi).

10.4.3 PARTIAL RESPONSE

To satisfy criteria for a PR, all of the following criteria must be met:

- No evidence of new disease:
- A change in disease status meeting ≥2 of the following criteria, with the exception that if only 1 parameter was abnormal before therapy, only 1 needs to improve:
 - o In a subject with baseline lymphocytosis (ALC ≥4 x 10^9 /L), a decrease in peripheral blood ALC by ≥50% from baseline; or a decrease to <4 x 10^9 /L;
 - A decrease by \geq 50% from the baseline in the SPD of the target nodal lesions and no new enlarged lymph nodes (diameter \geq 1.5cm);
 - o In a subject with enlargement of the spleen at baseline, a splenomegaly response as defined in Section 10.3.2;
 - In a subject with enlargement of the liver at baseline, a hepatomegaly response as defined in Section 10.3.2;
 - o A decrease by \geq 50% from baseline in the CLL/SLL marrow infiltrate or in B-lymphoid nodules.
- No target, splenic, liver, or non-target disease with worsening that meets the criteria for definitive PD
- Peripheral blood counts meeting 1 of the following criteria:
 - o Platelet count >100 x 10⁹/L or ≥50% increase over baseline without need for exogenous growth factors;
 - o Hemoglobin >110 g/L (11.0 g/dL) or ≥50% increase over baseline without red blood cell transfusions or need for exogenous growth factors (e.g., erythropoietin).

10.4.4 PARTIAL RESPONSE WITH PERISTENT LYMPHOCYTOSIS (PR-L)

Subjects who fulfill all the criteria for a PR but have not had a decrease in peripheral blood ALC by $\geq 50\%$ from baseline or a decrease to $<4 \times 10^9/L$ will be considered as a PR with persistent lymphocytosis (PR-L).

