Dosing of umbralisib initially occurred in the fasting state, but was transitioned mid-study to fed state dosing, with subjects instructed to take umbralisib with food. All dosing of umbralisib is now conducted using the micronized formulation and in the fed state.

Among 73 subjects in the modified ITT, which included subjects who received at least 800 mg/day of the original formulation or any dose of the micronized formulation and had at least one response assessment, 53 (73%) had reductions in disease burden, including 33 (45%) subjects with reductions of 50% or more, of which 3 (4%) were a CR and 30 (41%) were a PR. In subjects with relapsed or refractory CLL, 17 (85%) of 20 achieved an objective response, with 10 (50%) achieving an objective response per 2008 iwCLL criteria, 7 (35%) achieving a PR-L, and the remaining 3 (15%) achieving SD. Of 8 assessable subjects with CLL who had high risk cytogenetic features, 6 (75%) had a response, of whom 2 (25%) had a PR-L, and the remainder had SD. In subjects with FL, 9 (53%) of 17 subjects achieved an objective response, including 2 (12%) who achieved a CR; the remainder had PRs. In subjects with DLBCL, 4 (31%) of 13 achieved an objective response and 2 (15%) further subjects achieved SD. Responses for the other subject subgroups were HL: 1 CR, 4 SD, 4 PR; MZL: 1 PR, 4 SD; WM: 2 SD; and MCL: one PR, 4 SD, and 1 PD. In a post-hoc exploratory analysis, tumor reductions in most subjects with indolent lymphoma and CLL treated with umbralisib tended to improve over time. The mean DOR was 13.4 months (95% CI 7.7–19.1) in 16 subjects in the CLL cohort, 6.4 months (4.5– 17.3) in 4 subjects in the DLBCL cohort, and 9.3 months (3.6–15.1) in 9 subjects in the FL cohort. In a post-hoc exploratory analysis of PFS, median PFS was 24.0 months (95% CI 7.4 months-not reached) in 20 subjects with CLL, and 16 months (9.2 months-not reached) in 24 subjects with

U2-VEN-207

indolent NHL (FL, WM, MZL). Overall, umbralisib was well tolerated and displayed promising signs of clinical activity at the higher dosing cohorts.

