2.2 EFFICACY ENDPOINTS

Progression-free Survival (PFS)

PFS is defined as the interval from enrollment to the earlier of the first documentation of definitive disease progression or death from any cause.

Overall response rate (ORR)

ORR is defined as the proportion of subjects who achieve a CR, CRi, PR or PR-L.

Complete Response (CR) Rate

CR rate is defined as the proportion of subjects who achieve a CR or CRi.

U2-VEN-207

Dated: 05 October 2021 (Ver 4.0)

Page **38** of **112**

Rate of Undetectable Minimal Residual Disease (MRD)

Undetectable MRD is defined as the proportion of subjects who are MRD negative, defined as a quantitative detection of less than one CLL/SLL cell in 10000 leukocytes by flow cytometry (MRD level, 10^{-4}) in blood or BM.

Time to Response (TTR)

TTR is defined as the interval from enrollment to first documentation of CR, CRi, PR, or PR-L.

Duration of Response (DOR)

DOR is defined as the interval from the first documentation of CR, CRi, PR, or PR-L to the earlier of the first documentation of definitive disease progression or death from any cause.

Overall Survival (OS)

OS is defined as the interval from randomization (Phase 3 subjects only) to the first documentation of death from any cause.

U2-VEN-207

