10.4.5 STABLE DISEASE

To satisfy criteria for SD, the following criteria must be met:

U2-VEN-207

Dated: 05 October 2021 (Ver 4.0)

Page **78** of **112**

- No evidence of new disease:
- There is neither sufficient evidence of tumor shrinkage to qualify for PR nor sufficient evidence of tumor growth to qualify for definitive PD.

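### As written, PR-L is a subset of PR: some nodal or organ responders with persistent lymphocytosis are classed as stable disease, which can understate ORR

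*Combined protocol and SAP*

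**What the plan says.** Section 10.4.3 lists five parameters for PR: ALC, nodal SPD, spleen, liver and marrow infiltrate. It asks for "A change in disease status meeting ≥2 of the following criteria, with the exception that if only 1 parameter was abnormal before therapy", in which case one improvement is enough. PR also requires no new disease, no worsening to PD level, and an adequate platelet count or hemoglobin.

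Section 10.4.4 assigns PR-L to "Subjects who fulfill all the criteria for a PR but have not had a decrease in peripheral blood ALC by" at least 50% from baseline, or to below 4 x 10^9/L. The introduction in Section 10.4 words the category differently: it is "for subjects who have an elevated absolute lymphocyte count but otherwise meet all criteria for a PR".

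Section 10.4.5 makes SD the residual class: "There is neither sufficient evidence of tumor shrinkage to qualify for PR nor sufficient evidence of tumor growth" to be PD. Section 2.2 states "ORR is defined as the proportion of subjects who achieve a CR, CRi, PR or PR-L". Section 11.8 puts each subject in one category and lists PR and PR-L separately. Section 11.11.4 tests CR rate, uMRD, ORR and OS in that order after PFS, at two-sided 0.05, within each cohort.

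**The concern.** PR-L exists so that a response is not denied because lymphocytes remain raised, which Section 10.4.8 says can happen after umbralisib is started. The operative definition does not do this. It keeps the full PR count, and ALC is one of the items that can make up that count. The subject who most needs the category can therefore be the one it fails to admit, and two readers could class the same subject differently depending on whether they follow Section 10.4 or Section 10.4.4.

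At stake are ORR (a Phase 2 primary objective and a tested Phase 3 secondary that stands ahead of OS), and the date of first response that ends TTR and starts DOR. PFS does not depend on the PR/PR-L boundary.

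**Working it through.** **Step 1: the set relation.** As written, PR-L = (all PR criteria met) and (ALC has not fallen enough). Hence PR or PR-L = PR, and PR-L adds zero subjects to ORR. Subjects who do meet PR-L also meet PR, although Section 11.8 needs a single category.

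**Step 2: enumeration.** Assume ALC abnormal at baseline and still high, every other abnormal parameter responding, the blood-count criterion met, no sign of PD, and marrow not sampled.

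| Abnormal besides ALC (nodes, spleen, liver) | Needed | Met | Class as written | Class if ALC is set aside |
|---|---|---|---|---|
| none | 1 | 0 | SD | SD |
| exactly one | 2 | 1 | SD | PR-L |
| two | 2 | 2 | PR and PR-L | PR-L |
| three | 2 | 3 | PR and PR-L | PR-L |

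Only the second row is a lost responder. The one-parameter exception, "with the exception that if only 1 parameter was abnormal before therapy, only 1 needs to improve", does not apply there because two parameters were abnormal. A marrow improvement could supply the second item. In the Phase 3 schedule, however, baseline marrow is taken only when clinically indicated, and post-baseline marrow is required to confirm CR and for one MRD sample in blood-negative subjects. Phase 2 does require a baseline marrow.

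**Step 3: when the loss persists.** The first Phase 3 assessment is in the 14 days before Cycle 4, at 70 to 84 days (2.3 to 2.8 months). Section 10.4.8 says the lymphocytosis usually resolves in 3 to 4 months, so this assessment can fall before resolution. The next is before Cycle 12, at 294 to 308 days (9.7 to 10.1 months), then at least every 6 cycles. Section 10.4 uses best overall response, so a subject who is SD before Cycle 4 and whose ALC has fallen enough by Cycle 12 becomes PR and counts in ORR, but with first response recorded roughly seven months later. ORR itself loses the subject only if ALC stays high at every assessment, or if the subject progresses or leaves first.

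**Step 4: illustration of size.** The public text states no expected ORR, no ORR power, and no PR-L rate for U2 or U2-V, so there is no plan figure to reproduce. Suppose true ORR is p in both arms, a share x of Arm B is moved to SD, and none of Arm A is. With n per arm and m = p - x/2:

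- s0 = sqrt(2m(1-m)/n)
- s1 = sqrt(p(1-p)/n + (p-x)(1-p+x)/n)
- P(significant, favouring U2-V) = Phi((x - 1.96 s0)/s1)

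For n = 200, p = 0.90, x = 0.05: m = 0.875, s0 = 0.0331, s1 = 0.0330, and (0.05 - 0.0648)/0.0330 = -0.45, giving 33%. This is an unstratified approximation to the planned CMH test.

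| Assumed true ORR | n per arm | x = 0 | x = 1% | x = 2% | x = 5% |
|---|---|---|---|---|---|
| 95% | 200 | 2.5% | 6% | 13% | 47% |
| 95% | 150 | 2.5% | 6% | 11% | 38% |
| 90% | 200 | 2.5% | 5% | 9% | 33% |
| 90% | 150 | 2.5% | 5% | 8% | 26% |
| 62% | 200 | 2.5% | 4% | 6% | 17% |

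The 62% row uses the CLL/SLL response rate in the U2 dose-escalation study (Section 1.4); 90% and 95% are assumptions. Every x is an assumption. If x is zero there is no shift, and if it is equal in both arms the true rates stay equal and the test is not biased towards either arm.

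**The case against.** The strongest reply is that the literal reading is unreasonable. Section 10.4 describes subjects "who have an elevated absolute lymphocyte count but otherwise meet all criteria for a PR", which suggests that ALC is waived. If ALC is left out before abnormal parameters are counted, a subject with only nodes remaining fits the one-parameter exception. The earlier single-agent umbralisib study in Section 1.3.2.1 used the category additively: 10 of 20 responded by standard criteria, with "7 (35%) achieving a PR-L", giving 17 of 20. Section 11.8 also treats PR and PR-L as distinct. This shows what was probably intended. It does not settle the rule: neither Section 10.4 nor 10.4.4 says that ALC leaves the count, and 10.4.4, the operative definition, says the opposite.

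A second reply is that few subjects are affected. This largely stands. The gap needs exactly one non-ALC abnormality, no usable marrow comparison, and persistent lymphocytosis. Ublituximab, given in both arms, depletes lymphocytes quickly (Section 1.2.2), and best overall response allows later recovery. In Phase 3, ORR is tested only after PFS, CR rate and uMRD have succeeded. TTR and DOR are Phase 2 secondary objectives and lie outside the Phase 3 testing sequence.

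A reader might go further and infer that Arm B's ORR is understated, because only Arm A adds venetoclax from Cycle 4. That is plausible, but the documents do not support it as a finding. The rule is the same in both arms, treatment is identical through Cycle 3, and the pre-Cycle 4 assessment precedes any venetoclax. No persistence rate is given for either arm. The 35% figure comes from umbralisib without an anti-CD20 antibody and should not be carried over to U2.

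**Conclusion.** The definitions conflict and need correcting. As written, PR-L adds nobody to ORR, and a subject with lymphocytosis plus one other abnormal parameter, a response in that parameter, persistent ALC and no marrow credit is recorded as SD. This can understate ORR and delay the recorded first response.

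The number affected cannot be computed from the documents, and neither the existence nor the size of an imbalance between arms can be shown. The power table illustrates sensitivity only: with 5% of Arm B and none of Arm A misclassified at 200 per arm, the chance of a false ORR result favouring U2-V runs from 17% to 47% as the assumed true ORR goes from 62% to 95%, against 2.5% with no misclassification. It should not be cited as the expected bias.

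**What to change.** Reconcile Sections 10.4, 10.4.3 and 10.4.4 by rewriting 10.4.4:

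- ALC is set aside and the Section 10.4.3 count is applied to the remaining parameters: at least two improved, or one if only one non-ALC parameter was abnormal at baseline.
- All other PR criteria are met.
- ALC has neither fallen by at least 50% from baseline nor dropped below 4 x 10^9/L.
- PR and PR-L are mutually exclusive, in line with Section 11.8.

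The paragraph should also say how a marrow that was infiltrated at baseline but not repeated enters the count; otherwise such a subject could again need two improvements with only one assessed. Asking for just one non-ALC improvement in every case would go too far: with nodes and spleen both abnormal, PR-L would become easier to reach than PR.

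Align the Section 10.4 introduction and the IRC charter with the new text. The cost is one paragraph and a charter edit. No new data are needed, and assessments already read can be reclassified from the recorded measurements.

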10.4.5 STABLE DISEASE

To satisfy criteria for SD, the following criteria must be met:

U2-VEN-207

Dated: 05 October 2021 (Ver 4.0)

Page **78** of **112**

- No evidence of new disease:
- There is neither sufficient evidence of tumor shrinkage to qualify for PR nor sufficient evidence of tumor growth to qualify for definitive PD.

10.4.6 DEFINITIVE DISEASE PROGRESSION

The occurrence of any of the following events indicates definitive PD when compared with nadir values:

- Evidence of any new disease:
 - A new node that measures \geq 1.5 cm in the LD;
 - An increase by \geq 50% in greatest determined diameter of any previous site (\geq 1.5 cm);
 - New or recurrent splenomegaly, with LVD > 13 cm;
 - New or recurrent hepatomegaly, with LVD > 18 cm; Unequivocal reappearance of an extra-nodal lesion that had resolved;
 - A new unequivocal extra-nodal lesion of any size;
 - *New non-target disease (e.g., effusions, ascites, or other organ abnormalities related to CLL/SLL).

*Isolated new effusions, ascites, or other organ abnormalities are not sufficient evidence alone of PD unless histologically confirmed. Thus, a declaration of PD should not be made if this is the only manifestation of apparently new disease.

- Evidence of worsening of target lesions, spleen or liver, or non-target disease:
 - Increase from the nadir by \geq 50% from the nadir in the SPD of target lesions;
 - Increase from the nadir by \geq 50% in the LD of an individual node or extra-nodal mass that now has an LD of \geq 1.5 cm:
 - Splenic progression, defined as an increase in splenic enlargement by ≥50% from nadir (with a minimum 2 cm increase and LVD >13 cm);
 - Hepatic progression, defined as an increase in hepatic enlargement by ≥50% from nadir (with a minimum 2 cm increase and LVD >18 cm);
 - Unequivocal increase in the size of non-target disease (e.g., effusions, ascites, or other organ abnormalities related to CLL/SLL);
 - Transformation to a more aggressive histology (e.g., Richter's syndrome) as established by lymph node or other tissue biopsy (with the date of the biopsy being considered the date of CLL/SLL progression if the subject has no earlier objective documentation of CLL/SLL progression).
- Occurrence of cytopenias (decrease in platelet count or hemoglobin) directly attributable to CLL/SLL and unrelated to autoimmune cytopenias confirmed by BM biopsy showing an infiltrate of clonal CLL/SLL cells
 - The current platelet count is $<100 \times 10^9$ /L and there has been a decrease by $\ge 50\%$ from the highest on study platelet count at least 3 months after treatment;
 - o The current hemoglobin is <110 g/L (11.0 g/dL) and there has been a decrease by ≥20 g/L (2 g/dL) from the highest on study hemoglobin at least 3 months after treatment.

If there is uncertainty regarding whether there is true progression, the subject should continue study treatment and remain under close observation pending confirmation of progression. In particular, worsening of constitutional symptoms in the absence of objective evidence of worsening CLL/SLL

U2-VEN-207

will not be considered definitive disease progression; in such subjects, both CLL/SLL-related and non-CLL/SLL-related causes for the constitutional symptoms should be considered.

Worsening of disease during temporary interruption of study treatment (e.g., for intercurrent illness) is not necessarily indicative of resistance to study treatment. In these instances, CT/MRI or other relevant evaluations should be considered in order to document whether definitive disease progression has occurred. Subjects who meet the criteria for PD at any assessment may, in consultation with the Study Chair, remain on study for confirmation of PD at the following disease assessment. If subsequent evaluations suggest that the subject has experienced persistent definitive CLL/SLL progression, then the date of progression should be the timepoint at which progression was first objectively documented.

10.4.7 NON-EVALUABLE

In a subject who does not have evidence of PD, the occurrence of any of the following conditions indicates a response status of NE:

- There are no images or inadequate or missing images;
- Images of the liver and spleen are missing at that time point (with the exception that absence
 of splenic images will not result in an NE designation in a subject known to have undergone
 splenectomy).

A time point will be considered to have a response of NE if any target lesion is missing. PD may be assigned at any time point regardless of the extent of missing target or non-target lesions. Missing non-target lesions will not impact the ability to assess for response or disease progression.

10.4.8 LYMPHOCYTOSIS DURING THERAPY

[figure not shown]
Upon initiation of umbralisib, a temporary increase in lymphocyte counts (i.e., $\geq 50\%$ increase from baseline and above ALC of 5,000/mcL) may occur. The onset of isolated lymphocytosis usually occurs during the first few weeks of umbralisib therapy and usually resolves within 3 to 4 months. Subjects with lymphocytosis in the absence of other signs of progression should be continued on study drug until the occurrence of definitive disease progression (i.e., disease progression that is manifest by worsening CLL/SLL-related signs other than lymphocytosis alone), or the occurrence of another reason to discontinue study therapy.

U2-VEN-207

11 STATISTICAL CONSIDERATIONS

Details of the analyses will be provided in the Statistical Analysis Plan.

11.1 SAMPLE SIZE AND POWER

U2-VEN-207

11.2 GENERAL ANALYSIS CONVENTION

Unless otherwise stated, all analyses will be performed using SAS Version 9.2 or higher.

Summary tabulations will display the number of observations, mean, standard deviation, median, minimum, maximum, and appropriate percentiles for continuous variables, and the number and percentage by category for categorical data. Summaries will present data by cohort and overall, if appropriate. The data listings will include all available efficacy and safety data.

11.3 ANALYSIS POPULATION

The safety population will consist of all subjects who received at least one dose of study drug (ublituximab, umbralisib, or venetoclax). For the Phase 2 component, the ITT population will consist of all subjects who received at least one dose of each study drug (ublituximab, umbralisib, and venetoclax).

U2-VEN-207

For Phase 3, the ITT population will consist of all randomized subjects, regardless of administration of study treatment. Analyses of this population will assign subjects the treatment they were scheduled to receive, regardless of any errors of dosing or dose modifications. Subjects who received treatment in the group that is different from what they have been randomized to, will be noted in the clinical study report. The ITT population is the primary analysis population for efficacy analyses.

The per protocol population will include all ITT subjects without major protocol violations. Major protocol violations will be documented. Analyses based on per protocol population may be performed.

